All sites will have the most current version of this Pilot Study Protocol, informed consent documentation, and HIPAA authorization. All required approvals will be obtained at each location including the site's IRB of record (or affirmation to recognize the TAMU IRB as the IRB of record, or documentation of exemption from IRB approval). All planned modifications to the Protocol will be communicated to the various primary care sites in addition to the site's IRB of record and implemented, upon IRB approval if required. All engaged participating sites will safeguard data as required by their local information security policies and in compliance with HIPPA and General Data Protection Regulation standards. Through regular dialogue and open communication will be made so that all local site investigators conduct the study appropriately. All non-compliance with the study protocol or applicable requirements will be reported in accordance with local policy and as specified in the Protocol.

8. Study Timelines:

The duration of individual participation period in the study is limited to their medical encounter in the IPGx clinic, and any subsequent medication management visits their primary care physician refers back to the IPGx. No more than 180 days from the date of their enrollment in the study.

9. Variables and outcome measures:

- Frequency and nature of ADRs on the Naranjo Scale (19)
- Emergency department visits
- Hospital admissions
- Serum/plasma drug concentrations
- Pharmacogenomic genotype with corresponding ADR phenotype
- Drug-drug interactions, drug gene interactions, drug-drug-gene interactions

10. Procedures Involved:

Patients will be referred to the Texas A&M Interprofessional Pharmacogenomics Clinic (IPGx) by their primary care physicians to evaluate polypharmacy status, genotyping, pharmacokinetic/pharmacodynamic (PK/PD) assessment, and monitoring of potential for ADR.

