specified [in Exhibit A](#) [insert table or online reference to genotypes interpreted] will be conducted and a report generated (per the CPIC guidelines (20, 21)). In certain instances, blood or urine levels of drug or metabolites may need to be re-assessed periodically if warranted by standard clinical practice, on a case-by-case basis. If the physician wishes to determine whether a change in dose or a change in medication has resolved undesirable steady state levels of medications or their metabolites, a followup urine or blood sample (depending on the drug being measured and the specifications for the corresponding CLIA test for that drug) may be ordered in accordance with drug labels where dose titration is warranted, or where an actionable pharmacogenomic variant (under FDA and CPIC guidelines) indicates a change in dose or medication should be considered. The sample will be obtained in a timeframe the physician determines as medically prudent. Patients will be seen in the clinic after the final report is submitted to the referring physician.

There are inherent risks of morbidity and mortality associated with taking, changing or discontinuing medications in whatever standards-of-care are applicable to an individual's case. These risks are routinely weighted by the physician in the practice of medicine, and no actions beyond the exercise of physician judgments are prescribed under this protocol. IPGx will forward specific recommendations to the referring physician who in turn will make changes to the regimen, as desired. It is expected that changes made to mitigate a polypharmacy burden would reduce risk of ADRs. We do not expect these risks to differ from those inherent to the medication of choice and adjustments thereto during standard medical care.

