It should be noted that standard of care for changing most medications is simply trial and error (22), with a few exceptions warranting pharmacogenomic testing though consensus medical guidelines for actions based on results of pharmacogenomic exist and are endorsed by [Association for Molecular Pathology](#), [American Society for Clinical Pharmacology and Therapeutics](#), and the [American Society of Health-System Pharmacists](#). The working principle for this program is that the risks of being a polypharmacy patient without medication management care are greater than the risks of trying to ameliorate that burden with pharmacogenetic and drug level testing to inform medication management. In many respects that study can be viewed as a quality improvement project for participating clinics. For these reasons, the proposed study is one of minimal to no risk.

It is expected that study participants remain engaged with the primary care clinic from where they were referred. Since the period of study is 180 days and the recommendation calls for periodic re-evaluation of the enrollee, if concerns arise the referring clinician would help address the need to monitor safety. Lab data will be reviewed as it becomes available. We will establish a safety monitoring board constituted by team members to oversee and report any adverse events issues or episodes to the IRB. Because medication management is expected to align with standard of care and within normal parameters of physician judgment, the risk of adverse outcomes is minimal relative to a care plan that omits a medication management element and the polypharmacy and pharmacogenomics information that will be made available to the care team.

Data Safety Monitoring Plan.

Clinical study staff and investigators, under the supervision of the PI will review all data on an ongoing basis for data completeness and accuracy as well as protocol compliance. All data will be appended to the CSN Medical record and reconciled by [name], [name], or [name],

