- Changes of the study protocol raised by the review of the safety data;
- Suspension or early termination of the study because of serious concerns about subjects’ safety, inadequate performance, or rate of enrollment;
- Corrective actions regarding a study center whose performance appears unsatisfactory or appears to raise questions regarding the conduct of the study.
-

Immediate Action Report: The clinical Investigators will notify the PI and TAMU HRPP/IRB of any observations of a serious and immediate nature or recommendations to discontinue all or part of the study. In addition to verbal communications, recommendations to discontinue or

substantially modify the design or conduct of a study must be conveyed to the PI and the TAMU HRPP/IRB in writing by e-mail, fax, or courier within 5 business days of occurrence.

The study period is limited (one visit and 12 months of chart analysis), the number of subjects is small (n=22), and the risks to subjects are of low likelihood and low magnitude of harm, so stopping for futility is not justified.

14. Withdrawal of Participants:

An individual can be suspended or removed from the research protocol due to non-compliance with visits. Issues such as pregnancy, admission to hospice, death, will be evaluated by clinical staff in consultation with the principal investigator. Adverse Drug Responses (ADRs) as defined by Aronson: *“arise when a compound (e.g. a drug or metabolite, a contaminant or adulterant) is distributed in the same place as a body tissue (e.g. a receptor, enzyme, or ion channel), and the encounter results in an adverse effect (a physiological or pathological change), which results in a clinically appreciable adverse reaction.”* (26). For clarity, ADRs will not necessarily be a reason for removal of a subject from the study. An orderly termination procedure would include written notice and or documented phone call between the subject, their legal guardian, if appropriate, and a member of the care team. Enrollees will be given a two-week notice. The only safety reason for termination is the determination by the medical staff the patient's condition necessitates discontinuation of participation in the study. An example would be a determination by the physician that continued participation in the study would be deleterious to the enrollees' health. If a patient withdraws from the research, they will still be able to continue to be a patient at the IPGx.

15. Risks to Participants:

Risks involved:

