The likelihood of new risk is slightly increased in that test results could be erroneous or improperly rendered by the CSN. In such a case, the physician may choose a new standard of care medication while *misinformed* about the genotype of a patient. This is no worse than choosing a new standard of care medication while *uninformed* about the genotype of a patient. The likelihood of such errors is inherent in all CLIA tests that are used pervasively in the practice of medicine, and the probability and magnitude of risk to the patient is minuscule. One of the two principle of beneficence in the Belmont Report is to “maximize the possible benefit and minimize possible harms.” In the present case, the benefits of informing medication management far outweigh the inherent risks of making suboptimally informed medication management decisions (or doing nothing) when the medications the patient is currently taking are suspected of currently inflicting harm. Subjectively, the likelihood and magnitude of harm to subjects are low while the potential benefits are highly probable.

17. Potential Benefits to Participants:

The study is designed in alignment with the principles of *Standards in the Conduct of Registry Studies for Patient-Centered Outcomes Research – Report to PCORI* [11]. A description of the scope of the polypharmacy problem is described in more detail in Sections 3: Objectives, 4: Background, 9: Outcome measures, 13: Participant Safety.

Additionally, we seek to understand how and when polypharmacy begins the cascade of ADRs such as ED visits, falls, or expression of another comorbidity. Our expectation is that a patient will experience reduced polypharmacy burden, and that participation in a medication management program with pharmacogenomic and informed drug dose titration (when warranted), will reduce ADRs that are common and frequent in these populations. We also expect that participation will improve adherence.

The clinical burden of highly prevalent anticholinergic medications can be quantitatively monitored such that refined use of this class of drugs has substantial potential to inform and impact this major contributor to polypharmacy burden.

Benefits of the study for the healthcare and scientific communities

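### Section 14 lets participants be removed from the research for missed visits, although part of the outcome data comes from charts; this could selectively lose follow-up that needs no visit

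*Protocol*

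**What the plan says.** Section 14 (Withdrawal of Participants) states: "An individual can be suspended or removed from the research protocol due to non-compliance with visits". The wording is permissive. It gives no number of missed visits and no list of required ones. It adds that someone who withdraws from the research may remain a clinic patient, but does not say whether research chart review continues.

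The Protocol is not uniform on which visits there are:

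- Section 8 limits participation to the IPGx encounter plus "any subsequent medication management visits their primary care physician refers back to the IPGx", and caps it: "No more than 180 days from the date of their enrollment in the study".
- Section 13, in the monitoring plan, says: "The study period is limited (one visit and 12 months of chart analysis), the number of subjects is small (n=22").
- Section 10 expects a return contact: "Patients will be seen in the clinic after the final report is submitted to the referring physician".
- Section 13 also says that "the recommendation calls for periodic re-evaluation of the enrollee".

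Section 9 lists ADR frequency and nature, emergency visits, admissions, drug concentrations, genotype with ADR phenotype, and interactions. Section 10 names self-report and documentation as the ADR sources, and lists urgent-care and hospital records and visit summaries. Section 11 has clinical documents imported from the Family Care Clinic.

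**The concern.** Whether a patient attends a return visit and whether that patient's emergency visits, admissions and charted ADRs can be observed are separate matters here. Much of the second comes from the record. A rule that ends research participation because of the first can end the second without need.

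The loss is unlikely to be random. Section 17 names problems arising from non-compliance among the drivers of high healthcare use, and Section 4 associates polypharmacy with poorer adherence and with hospitalization. Missing a visit is not the same as missing medication. On the Protocol's own premises, though, patients who miss visits could plausibly have more events than those who attend. Event frequency computed on those who remain would then be too low.

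Because neither the required visits nor a threshold is stated, removal is left to case-by-case judgement, and two similar patients could be handled differently.

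**Working it through.** The Protocol states no removal rate, event rate or sample-size calculation, so there is no figure to reproduce. The check has two parts.

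**1. What needs a visit**

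- Emergency visits and admissions: readable from records.
- ADRs: the documented part is readable from records; the self-reported part needs contact.
- Genotype: one test from the initial swab (Section 10), so later attendance does not matter.
- Drug concentrations: need a sample.

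The rule therefore puts at risk follow-up on two listed outcomes and part of a third that no visit is needed to obtain.

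**2. What the loss could do (assumed values)**

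Let f be the fraction removed, p the event risk in retained patients and k the risk ratio, removed to retained. Assume that removed patients contribute no data.

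- Full-cohort risk = (1 − f)p + f·k·p = p[1 + f(k − 1)]
- Reported risk = p
- Relative understatement = f(k − 1) / [1 + f(k − 1)]

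Results:

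- k = 1, any f: 0.
- f = 0.1, k = 1.5: 0.05/1.05 = 4.8%.
- f = 0.2, k = 2: 0.20/1.20 = 16.7%. With p = 20%, the full-cohort risk is 0.8 × 0.20 + 0.2 × 0.40 = 24%, against 20% reported.
- f = 0.3, k = 2.5: 0.45/1.45 = 31.0%.

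In percentage points, with m of N removed, the understatement is p(m/N)(k − 1). The width between assuming that none and that all of the removed patients had the event is m/N. Take p from 0.2 to 0.4 and k from 1.5 to 2.

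- N = 22 (Section 13), m = 2, 4 or 7: widths 9.1, 18.2 or 31.8 points. Understatement runs from 0.2 × (2/22) × 0.5 = 0.9 to 0.4 × (7/22) × 1 = 12.7 points.
- N = 50 (the maximum in Section 6), m = 5, 10 or 15: widths 10, 20 or 30 points. Understatement runs from 0.2 × 0.1 × 0.5 = 1 to 0.4 × 0.3 × 1 = 12 points.

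At k = 1 only precision suffers. With 4 of 22 removed, the standard error grows by √(22/18) = 1.11, about 11%.

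If these patients stay in chart follow-up, m = 0 for chart-based outcomes, and both the bias and the width due to this rule vanish.

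**The case against.** The strongest reply is that Section 14 is discretionary, offers suspension as an alternative and gives two weeks' notice. It does not say that chart review stops, that earlier data are discarded or that the patient leaves the denominator. If later visits happen only on referral, many patients have no later visit to miss, and few might be removed. Events charted before removal may still count, which would shrink the figures above. This is also a single-arm pilot of at most 50 with no comparison group.

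Most of that stands, and it limits the point to a risk: the rule can cause selective loss, and the documents do not show that it will. It does not justify the rule. Removal from the research naturally reads as an end to observation, nothing provides otherwise, and Section 12 confines use of the data to the Protocol's scope. Whom to follow is a protocol decision; a later analysis plan cannot recover charts that were never reviewed.

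A reader might infer three stronger things that the documents do not support:

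- That removal makes retention look better. Removals are attrition, and Section 13 requires retention and attrition in the study reports, so removal would worsen reported retention.
- That the rule contradicts an adherence outcome. Section 17 says "We also expect that participation will improve adherence", but as an expected benefit; adherence is not among the Section 9 outcomes.
- That all return visits are optional, or all outcomes chart-based. Sections 10 and 13 expect some return contact, and drug concentrations and self-reported ADRs need it.

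**Conclusion.** The point holds as a design weakness worth correcting. Section 14 allows removal for missing visits that are not defined, in a study where part of the outcome data needs no visit, and it makes no provision for continued chart follow-up. Applied, the rule could lose that follow-up selectively.

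The 5% to 31% relative understatement rests wholly on assumptions: 10% to 30% removed, 1.5 to 2.5 times the retained risk, and no data from removed patients. At equal risk the bias is zero; if those who miss visits had fewer events, its direction would reverse. That chart data end on removal is an inference from the wording and from the absence of any contrary provision.

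**What to change.** In Section 14, delete missed visits as a ground for removal from the research. State that a participant who misses visits stays enrolled and is followed by chart to the end of the observation window, unless consent is withdrawn or another Section 14 ground applies. Keep every enrolled participant in the denominator for chart-based outcomes.

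Reconcile the 180-day limit in Section 8 with the 12 months of chart analysis in Section 13, since the end of follow-up is otherwise undefined. Reconcile also the statements in Sections 8, 10 and 13 on return contact, so that a missed visit has a definite meaning when it is recorded.

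The cost is one paragraph in Section 14, the alignment of those statements and a little more chart review of a kind already planned. Drug concentrations and self-reported ADRs will still be missing for patients who do not return.

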Goldblatt Systems LLC. The Goldblatt Systems LLC CSN Electronic Health Record will be used in the Precision Medication Management Practice and PHI/ePHI will be housed by Goldblatt in accordance with the BAA. The CSN in Tucson is HIPPA and ONC (Office of the National Coordinator for Health Information compliant). Goldblatt Systems LLC, as a small company, maintains no formal scientific/ethics policy. In the Tucson Office Goldblatt Systems has a staff of approximately 20 people, some of whom have worked with [name] for many years prior, including Chief Technical Officer [name] and the Director of Engineering. The team includes software engineers, content subject matter experts, implementation staff, and quality control and assurance staff. In Pennsylvania, [name] employs approximately 20 people as well, which consist of world-class PhD's from places such as Johns Hopkins who have expertise in genomics, toxicology, mass spec, and includes operating various genetic arrays. At InnovativeGx in San Antonio, and IC42 in Aurora CO, there are several pathologists who have laboratory, toxicology, or forensic expertise. Goldblatt systems LLC has a clinical pharmacist (PharmD) on staff, in addition to business development legal and support personnel.

InnovativeGx is a CAP/CLIA and ABFT certified clinical diagnostics laboratory. In terms of research related activity outside the institution, please see 12.0 Data and Specimen Banking. The Texas lab is CAP CLIA, and ABFT certified. Lab specimens for pharmacogenomics would be handled off-site in Innovative Gx's San Antonio, TX clinical lab.

IC42 is a CAP/CLIA and ABFT certified clinical diagnostics laboratory. In terms of research related activity outside the institution, please see 12.0 Data and Specimen Banking. The Colorado lab is CAP CLIA, and ABFT certified. Lab specimens for drug blood levels (derived from urine levels in this study) would be handled off-site in IC42's Aurora, Colorado clinical lab.

22. Prior Approvals

IRB approval of this protocol, and amendments hereto, will be obtained from Texas A&M IRB, and any IRB of future collaborative health systems and research institutions.

23. Confidentiality

Please see above 7, 11, 12, 13 and 19

- *Where and how data or specimens will be stored locally?* Any samples will be collected at the Texas A&M Family Medicine Clinic using biosafety compliant collection kits provided by IC42, and InnovativeGx, and shipped immediately standard shipping. Then the samples will be handled at IC42 and InnovativeGx, in accordance with a fully certified lab. Specimens for this pilot study will not be entered into a biorepository.
- *How long the data or specimens will be stored locally?* Specimens will be confidentially stored at IC42 and InnovativeGx, until analysis and destroyed after usable results are generated.
- *Who will have access to the data or specimens locally?* Nobody will have access to the specimens locally other than the phlebotomy staff at the TAMU phlebotomy lab. Data within the CSN is available to authorized providers and personnel with a password.
- *Who is responsible for receipt or transmission of the data or specimens locally?* A phlebotomy staff member at the TAMU phlebotomy lab will ship specimens using the kits provided by IC42 and InnovativeGx. . Test results will be sent directly to TAMU Family Medicine and uploaded into the CSN by an investigator on this protocol or authorized staff under his/her supervision and accessed by TAMU staff and Investigators through secure access to the CSN .
- *How data and specimens will be transported locally?* There will be no local transport of specimens. Data will be stored in the CSN on the cloud.
- This CSN Module is 2015 Edition compliant and has been certified by an ONC-ACB in accordance with the applicable certification criteria adopted by the Secretary of Health and Human Services.
- <https://www.goldblattsystems.com/wp-content/uploads/2020/01/Goldblatt-2015-Edition-Certificate-1.pdf>

24. Provisions to Protect the Privacy Interests of Participants:

We will obtain written informed consent for participation, interaction, and collection of medical data from a patient. No participant will be required to interact with anyone or share personal information with anybody other than their care team providers at their referring clinic and the Texas A&M IPGx staff. See exclusion criteria about unwillingness to participate or consent. Participants will be made to feel at ease through open communication with Texas A&M IPGx staff and explanation of data use sharing and limitations thereof in the informed consent form. Participants should feel no more or less uncomfortable than when presenting to any general medicine clinic. There is nothing invasive to worry about other than giving urine and a buccal swab. Discomfort about sharing DNA information can be addressed in the informed consent form and consultation. Participants will be advised that their information will always be handled

confidentially. Data will be protected by the lab, and within their medical record, in accordance with federal privacy laws. The genetic material obtained (see 12 above) will only be used to determine a patient's enzymatic handling of medications. The test to be administered will not delve into someone's heritage, or other sensitive information, beyond what they consent to. Authorized members of the research and care team will have a password so that they can access the secured electronic health record.

25. Compensation for Research-Related Injury

N/A

Medication management decisions are up to the referring physician or the IPGx clinic physician (if appropriate).

While outcome data will be collected, this protocol is not intended to evaluate or propose any experimental intervention outside standard of care (i.e., drugs for FDA approved indications, or off label use at the discretion and direction of the prescribing physician).

26. Economic Burden to Participants

Transportation to the clinic. The possible need to go to a pharmacy and pick up a new prescription. The costs of the tests will be supported by Texas A&M. Doctor visits will be billed to their health insurance carrier.

27. Recruitment Methods

(Describe when, where, and how potential participants will be recruited.) [name] has identified 22 of his patients who might benefit from participation in this IPGx Pilot study. Research recruiting will be performed by Drs. [name] and [name] and their staff using email, telephone calls, or in-clinic discussion as warranted for each patient. The collateral materials used will include a call/in person script, an email script, and a general brochure about clinical research participation.

Subject compensation not contemplated.

28. Consent Process

We will obtain consent in a basic informed consent form [**Appendix 1**].

An individual team member authorized by the principal investigator and IRB can obtain consent from patients. Regardless of who is obtaining consent, the Principal Investigator is responsible to ensure the correct procedures are carried out.)

- **Where will the consent process take place?** At the designated IPGx (Interprofessional Pharmacogenomics Clinic) or Family Care Clinic.
- **Any waiting period available between informing the prospective participant and obtaining the consent?** It would be at the discretion of the patient to consent when they decide they are comfortable participating.

- Any process to ensure ongoing consent? If any material changes to the research or significant findings that could affect their willingness to continue participation in the study, subjects will be notified. Participants may end their participation at any time.
- The role of the individuals listed in the application as being involved in the consent process. The role of the PI would include: answering an enrollee's questions, discussing risk - benefit options and alternatives, and reporting back to the team. A patient consent to participate will be obtained in writing.
- The time that will be devoted to the consent discussion. As much as needed, 1 hour estimated, inclusive of medical history and prescription information collection.
- Steps that will be taken to minimize the possibility of coercion or undue influence. We can make it clear at the outset that this is completely voluntary, and the consent form will emphasize this. It will not in any way jeopardize the patient's relationship with their doctor or anyone else. No financial inducements will be used.
- Steps that will be taken to ensure the participants' understanding.) Patient will acknowledge in writing they understand. There can be a translator if needed for Spanish speaking subjects on select clinic days.

Waiver or Alteration of Consent Process:

NA.

Participants who are not yet adults (infants, children, teenagers)

N/A.

This study will focus on older adults.

Cognitively Impaired Adults

Consent of such subjects will be done in accordance with Texas A&M policies, ethics, culture, and legal considerations.

Adults Unable to Consent

N/A, to be excluded. See inclusion/exclusion criteria

30. Process to Document Consent in Writing:

See Appendix 1- Informed Consent Form

31. Drugs or Devices:

Electronic Medical record

It should be noted that the FDA has a current posture of not regulating physician facing clinical decision support tools (24). However, the FDA has issued nonbinding guidance (25) for Software as a Medical Device (SaMD) that recommends design control and clinical evaluation standards, including the use of third-party certifications, for SaMD. While the CSN and the pharmacogenomic dashboards being used in this protocol are not subject to FDA regulation under the SaMD framework (as for electronic medical record readouts), the CSN platform has received [certification](#) from rigorous third party (ONC-Authorized Certification Bodies) evaluation.

Pharmacogenomic Testing

The pharmacogenomic tests being conducted by InnovativeGx, are lab developed tests (LDT) marketed under the Clinical Laboratory Improvement Amendments (CLIA) under the jurisdiction of the Centers for Medicare and Medicaid Services. Most medical decision making is based on LDT tests marketed under the CLIA framework, which covers about 260,000 laboratories in the US, and interpreted by physicians (and pharmacists) within the statutory scope of practice and accepted medical guidelines. Most clinical DNA sequencing and especially, pharmacogenomic are commonly made available under the LDT-CLIA regulatory framework and used in accordance with established consensus medical guidelines. Consensus medical guidelines for actions based on results of pharmacogenomic exist, are curated by the Clinical Pharmacogenetics Implementation Consortium ([CPIC](#)), and are endorsed by Association for Molecular Pathology, American Society for Clinical Pharmacology and Therapeutics, and the American Society of Health-System Pharmacists.

Clinical Pharmacokinetic Tests

